The target quit date session will be scheduled to occur up to 2 weeks following the pre-quit session. Prior to the booster counseling sessions, self-reported smoking will be assessed (time line follow back, CO, saliva cotinine and urinary cotinine); we will also administer self-report questionnaires (e.g., smoking urges, withdrawal and mood). Days to relapse (primary outcome) will be defined as number of consecutive days prior to 7-day relapse (7 consecutive days of smoking). Participants will then meet with a smoking cessation counselor for a 15 minute booster counseling session. Participants will receive small monetary incentives for each week of biochemically confirmed abstinence based on CO level (<=5ppm) and/or urine cotinine assessment (NicAlert, Nymox Pharmaceutical Corporation, Hasbrouck Heights, NJ) that also indicates no smoking during the past 7 days (\$75/week). Participants will be paid in cash after abstinence has been verified (and will not be paid for a missed visit). There is a \$50 bonus for participants who have attended at least 4 of the 5 in-person monitoring visits. Telephone assessments and counseling may be provided if participants miss a visit, at the discretion of the PI.

6 Month Follow-up (~Week 28). Participants who are biochemically verified to be quit at MV5 will be contacted 24 weeks post TQD by telephone to complete a brief survey of their smoking practices using the timeline follow-back assessment. Those who report not smoking a cigarette for at least the past 7 days prior to completing the survey will be asked to come to the Center for biochemical verification of smoking status by providing CO, saliva cotinine and a urine cotinine sample.

12 Month Follow-up (~Week 52). Participants who completed all visits up to and including the Pre-Quit visit will be contacted 48 weeks post TQD by telephone to complete a brief survey of their smoking practices and eating behavior. All measures collected at the 6 Month Follow-up will be collected with the addition two questions about readiness and intention to quit smoking (if applicable).

Table 2. Measures and Time Points

Activity	Phone Screen	Intake	fMRI Scans	Pre-Quit	TQD	MV 1-5	Follow-up	12-month Follow-up
Weeks	-1	0	1, 2	3	4	5, 6, 7, 8	28	52
Demographics		X						
Urine drug screen		X	X					
Urine pregnancy screen		X	X					
ETOH history/BrAC		X						
Height		X						
Weight		X						
Smoking behavior (FTND)		X						
Medical history form		X						

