Salivary testosterone: Salivary testosterone will be used to control for between-session differences that may occur due to change in testosterone levels in male and female participants. Testosterone (pg/ml) will be collected at the start of the scan session. Approximately 2 ml of saliva will be collected using a passive drool method and saliva collection aid (Salivette LLC, State College, PA, USA). The saliva will be stored in plastic vials at –20°C. Saliva samples will be assayed using testosterone EIA kits (Salimetrics LLC, State Collect, PA, USA). Salivary testosterone is highly correlated with plasma testosterone [55].

fMRI Measures: See fMRI Scanning Sessions above.

Primary Outcomes (Main Study): Multiple measures of abstinence will be measured for this study. The primary outcome will be the number of days to relapse following the target quit date. Relapse will be confirmed using a conventional SRNT guideline criterion of either a positive biochemical verification of smoking [3, 56] or 7 consecutive days of smoking based on self-report (it is very unlikely that a subject would meet the latter criterion without also meeting the former, given the long half-life of cotinine). The days to relapse will be based upon time from target quit date to the first day of the relapse period. Self-reported daily smoking data will be collected using a validated timeline follow-back method [57]. Self-reported abstinence will be biochemically verified on a weekly basis using urine cotinine (<100ng/ml) [56] and a CO reading

of ≤5PPM. Drop-outs will be considered relapsers following the last date of abstinence data provided [7, 58]. Secondary outcomes will include days to first “slip”, and cross-sectional measures of 7-day and 30-day point prevalence (biochemically verified weekly with cotinine, which provides an assessment of smoking in the last 7 days).

Carbon Monoxide (CO): The CO monitor is a handheld device that uses a disposable mouthpiece, reports CO in parts per million (ppm), and takes about 5 minutes to administer. Carbon monoxide measurements will be collected from smokers at each visit as a biochemical verification of smoking exposure.

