Smoking Urges/Craving: The 10-item brief QSU-B questionnaire on smoking urges [61] will be administered at the same time points to assess cravings to smoke. The QSU-B contains 2 subscales (anticipation of reward, relief from negative affect). During the fMRI scans (prior to and following the cue reactivity task), participants will also be asked to rate the severity of their urges to smoke using two 4-point Likert scale items: “cravings for a cigarette” and “urges to smoke at this time” (0=not present, 3=severe). These 2 items have been related to smoking cessation outcomes [62] and resting cerebral blood flow in our prior study [63], and are feasible to assess as a brief measure in the MRI scanner.

Stress/Anxiety: Anxiety will be measured at both fMRI scanning sessions using the State-Trait Anxiety Index [64], which has been used as a covariate in fMRI studies of stress response [52].

Participants will be asked to rate “how stressed do you feel right now” on a scale from 0-100 immediately before and after the MIST.

Readiness/Intention to Quit Smoking: two questions will be asked at the 12-month follow-up survey to assess readiness to quit smoking and intention to quit smoking. The readiness questions is asks on a Likert scale from 1 – 9 the participant’s current thinking about smoking (1 = taking action to quit, 9 = no thought of quitting). The intention to quit smoking questions asks how likely the participant is to try to quit in the next 30 days on a Likert scale from 1 -- 4 (1 = very unlikely, 4 = very likely). The two questions will be asked regardless of study-quit status.

Secondary Subjective Outcomes (Recruitment & Retention Pilot Study):

Impressions of Research: Attitudes towards research; motivations for participation; perceived risks/benefits of research; personal financial wellbeing and perceptions of influence or coercion will be assessed via text survey at baseline (following phone screen), mid-way through participation and at study completion. Study staff will attempt to contact subjects who withdraw or are lost-to-follow up to identify reasons for withdrawal. We will assess overall satisfaction with the study, acceptability of the frequency and content of messages (IP and IC groups only). For all models, a term will be included for individual study as well as other relevant covariates (e.g., sex, age, income).

2. Statistical Analysis

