- requires or prolongs hospital stay
- results in persistent or significant disability or incapacity
- a congenital anomaly or birth defect
- an important medical event

Important medical events are those that may not be immediately life threatening, but based upon appropriate medical judgment may jeopardize the subject, and may require intervention to prevent one of the other serious outcomes noted above. For example, drug overdose or abuse, a seizure that did not result in in-patient hospitalization, or intensive treatment of bronchospasm in an emergency department would typically be considered serious. All adverse events that do not meet any of the criteria for serious will be regarded as **non-serious adverse events**.

Collection and Recording of AEs and SAEs.

Adverse Events and SAEs will be collected by spontaneous self-report.

Research staff are trained to inquire (time of onset, nature of issue reported, possible relation to study, review of previously reported side effects or concerns, concomitant medications, severity/intensity, etc.) about any notable side effects or medical concern reported by participants. Side effects will be rated by participants utilizing the following severity scale: 0 (None=No Concerns), 1 (Mild=Side Effect or event does not interfere with usual daily activities), 2 (Moderate= Side effect does interfere with some activities), and 3 (Severe=No normal activities are possible). Any severe (or a pattern of modern) side effects or notable medical concerns will be reported to the Project Manager, Study Physician, and Principal Investigator to determine a course of action and relationship (causality) to the study procedures. This

consultation, including all relevant information will be documented via email. The clinical course of each event will be followed until resolution, stabilization, or until it has been determined that the study treatment or participation is not the cause.

Information surrounding AEs and SAEs are recorded and secured within the appropriate source documents (i.e. subject chart), Case Report Forms (e.g. SEC form, etc.) when applicable, an AE note or SAE report, and the AE/SAE log within the Study Administrative File.

Documentation of AEs will include the following information:

- Protocol name
- Subject identifier
- Description of the event
- Date and time of onset and outcome
- Intensity/Severity
- Action taken
- Relationship (causality) to the study
- Outcome

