Documentation of SAEs will include the following information:

- Protocol name
- Subject identifier
- Description of the event
- Date and time of onset
- Current status
- The reason why the event is classified as serious
- Action taken
- Investigator assessment of the association between the event and study treatment
- Welfare of subjects/Outcome
- Follow-Up Plan (if applicable)

Management of SAEs or Other Study Risks.

The Study Physician will oversee the management of all SAEs and other study risks. SAEs will be monitored closely until the event has been stabilized and/or the subject has been referred to the care of their primary care physician. The Study Physician will also review data collected during the medical history portion of the Intake Visit for all subjects who experience a SAE and, when required, will provide follow-up consultation with the participant. All instances of consultation will be recorded.

AE, SAE, and Unanticipated Problems Reporting.

The procedures for unanticipated problem, adverse event, and serious adverse event reporting are consistent with NIH and UPenn-specific guidelines and are as follows:

1. Alert the IRB of any and all reports of unanticipated problems involving risk to subjects or others, AEs, and SAEs when appropriate (i.e. within 10 business days, summary at continuing review, etc.). AEs and SAEs meeting reportable event/unanticipated problem guidelines (unexpected and related) will be submitted to the appropriate IRB within 10 business days of occurrence using the on-line system. If an AE/SAE involved a death and indicates that participants and others are at an increased risk of harm, the event will be reported to the IRB within 3 days.
2. Inform applicable members of the study team of any and all reports of adverse events.

In addition to unanticipated problems (including applicable AEs and SAEs), the following events will be promptly reported to the IRB within 10 business days:

1. Any adverse experience that, even without detailed analysis, represents a serious unexpected adverse event that is rare in the absence of drug exposure (such as agranulocytosis, hepatic necrosis, Stevens-Johnson syndrome).
2. Any adverse event that would modify the protocol or informed consent form, or would prompt other action by the IRB to assure protection of human subjects.
3. Information that indicates a change to the risks or potential benefits of the research, in terms of severity or frequency. For example:

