 - An interim analysis indicates that subjects have a lower rate of response to treatment than initially expected.
 - Safety monitoring indicates that a particular side effect is more severe, or more frequent than initially expected.
 - A paper is published from another study that shows that an arm of your research study is of no therapeutic value.
4. Change in FDA safety labeling or withdrawal from marketing of a drug, device, or biologic used in a research protocol.
5. Breach of confidentiality.
6. Change to the protocol taken without prior IRB review to eliminate apparent immediate hazard to a research subject.
7. Incarceration of a subject when the research was not previously approved under Subpart C and the investigator believes it is in the best interest of the subject to remain on the study.
8. Complaint of a subject when the complaint indicates unexpected risks or the complaint cannot be resolved by the research team.
9. Protocol violation (meaning an accidental or unintentional deviation from the IRB approved protocol) that in the opinion of the investigator placed one or more subjects at increased risk, or affects the rights or welfare of subjects.

5. Management of Information for Multi-center Research where a Penn Investigator is the Lead Investigator of a multi- center study, or Penn is the lead site in a multi-site study.
Not applicable.

6. Risk/Benefit Assessment

Research staff will monitor subjects closely during their participation. Thus, the risk to benefit ratio for this project is perceived to be low and justifies its implementation.

SUBJECT COMPENSATION

Participants will be compensated for the time and effort required to complete study procedures. Participants will be given the means to travel to and from their appointments at no cost to them. Participants will be given two options for travel coverage: 1) participants may elect to receive a flat rate of \$10/day to cover their travel expenses to and from the center or 2) participants may elect to use a round-trip ride service (i.e. Lyft.) which will be arranged and paid for in full by the research study. If participants choose to use the ride service, they will not receive \$10 for their travel reimbursement.

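### Adverse events rest on spontaneous self-report with no scheduled question and only discretionary contact after a missed visit, so a death or medical drop-out while abstinent may be missed as an SAE and counted as a relapse

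*Combined protocol and SAP*

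**What the plan says.** **Collection.** Under Data and Safety Monitoring (Collection and Recording of AEs and SAEs): "Adverse Events and SAEs will be collected by spontaneous self-report". Staff then inquire "about any notable side effects or medical concern reported by participants", so the inquiry follows something the participant has already raised. Table 2 has no adverse-event row.

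**Definition.** The SAE list in the same section includes fatal events and any event that "requires or prolongs hospital stay".

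**Missed visits.** Under Monitoring Visits During 30-Day Abstinence Period: "Telephone assessments and counseling may be provided if participants miss a visit, at the discretion of the PI".

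**Outcome scoring.** Under Primary Outcomes (Main Study): "Drop-outs will be considered relapsers following the last date of abstinence data provided". Neither that section nor the Aim 1 analysis (Cox regression on a censored time to event) has a rule for death or medical exit.

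**Reporting.** Under AE, SAE, and Unanticipated Problems Reporting, events that are both unexpected and related "will be submitted to the appropriate IRB within 10 business days of occurrence using the on-line system". Deaths that also point to increased risk for others have a 3-day limit.

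**Later contact.** The 6-month call goes only to those verified quit at Monitoring Visit 5. The 12-month call goes to everyone who completed visits through Pre-Quit. Among the pilot study's secondary outcomes the plan adds: "Study staff will attempt to contact subjects who withdraw or are lost-to-follow up to identify reasons for withdrawal".

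**The concern.** These provisions depend on one another. The SAE definition covers events that a participant may be unable to volunteer, and a participant who has died cannot volunteer anything. For such a person the first sign the team sees may be an absence. The plan does not require anyone to follow up that absence. If it ends in drop-out, the default record is a relapse.

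Two things are at stake. The safety record could omit the most serious events. The primary outcome could also contain relapses that did not happen. Because the call is discretionary, the same kind of absence could yield smoking data for one participant and an imputed relapse for another.

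**Working it through.** The plan gives no figure on this point to reproduce. The first step compares the passages, and the second sizes the effect on the primary analysis.

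**Step 1. Is there another route by which an SAE would be found?**

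| Contact or tool | Stated purpose | Would it find a death or medical exit? |
|---|---|---|
| Visits in Table 2 | Smoking, mood, withdrawal and urge measures | Only if the participant attends and volunteers it |
| Call after a missed monitoring visit | Assessment and counselling | Not assured, because optional |
| Contact with withdrawn or lost participants | Reason for withdrawal | Possibly, but placed under the pilot and not described as SAE collection |
| 6-month call | Smoking survey, MV5-verified quitters only | Possibly, no adverse-event item |
| 12-month call | Smoking and eating survey, all who completed Pre-Quit | Possibly, late, no adverse-event item |
| Emergency Contact Form | Emergencies at the scanner | Not its stated use |

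Several contacts could bring an event to light by chance. None is described as collecting SAEs, and none is a stated route for learning of a death.

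**Step 2. When would such a person count as relapsed?** Relapse requires a positive biochemical test or seven straight days of self-reported smoking. Otherwise it is imputed, and only for drop-outs. A false relapse therefore needs three things together: the participant is still abstinent, the medical event ends participation, and the person supplies no later smoking data.

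**Step 3. Size of the effect on the Aim 1 Cox analysis.** Inputs from Power and Sample Size Considerations: N = 200, alpha 0.0085, 80% power, one-sample effect 0.25 or hazard ratio 1.32. Assumptions: a two-sided test, and a hazard ratio per standard deviation of the predictor.

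- Check of the plan's own figure: n = (z for alpha + z for power)² / d² = (2.6315 + 0.8416)² / 0.25² = 12.06 / 0.0625 = 193.0, so 194 (197 by the noncentral t). Power at n = 200 is 80.9%. The stated 200 and 80% agree.
- Events needed for hazard ratio 1.32: 12.06 / (ln 1.32)² = 12.06 / 0.0771 = 156.5, so 157, about 78% of 200. The plan states no relapse rate, so 157 is used as the event count.
- Suppose m of the 157 events are false and unrelated to the predictor, and the log hazard ratio shrinks by (157 − m)/157. Then power = Φ(√157 × 0.2776 × (157 − m)/157 − 2.6315).
- If those m participants were instead censored, events fall to 157 − m and the hazard ratio stays at 1.32.

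| False relapses m (assumed) | Hazard ratio if counted | Power if counted | Power if censored |
|---|---|---|---|
| 0 | 1.320 | 80.2% | 80.2% |
| 1 | 1.318 | 79.5% | 79.8% |
| 2 | 1.315 | 78.9% | 79.5% |

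Counting one or two such cases as relapses costs about 0.6 or 1.3 points of power. Censoring them would recover about half of that.

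**The case against.** The case on the other side is substantial. This is an observational study with no drug or device, described as minimal risk, in healthy adults aged 18 to 65 with long exclusion lists. Spontaneous reporting is defensible in that setting. The main foreseeable harms are already solicited: the withdrawal scale is given at all visits, and stress is assessed after each scan and again before the participant leaves. Scoring drop-outs as relapsed is a stated, referenced convention, and censoring medical exits brings its own assumption of non-informative censoring. The safety section also names a side-effect case report form whose content is not shown, so Table 2 may not list everything that is asked.

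Most of this stands, and it rules out several stronger readings that a reader might infer.

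- *That deaths and hospitalisations will not be found.* A hospitalised participant can report at a later visit or call, and lost participants may be contacted. The supportable statement is that such events may be missed.
- *That a missed visit is scored as a relapse.* The rule applies to drop-outs. Someone who returns and completes the timeline follow-back is not one, and someone who had already relapsed is unaffected.
- *That the IRB deadline fails through most of follow-up because scheduled contacts are far apart.* Spontaneous reports are not tied to visits, and the 10-business-day rule covers only unexpected and related events. Related events should be rare when only calls and one verification visit remain.
- *That the frequency trigger cannot work.* The trigger is "Safety monitoring indicates that a particular side effect is more severe, or more frequent than initially expected", offered as an example. It can operate for withdrawal and scan-day stress, which are solicited.
- *That the zero level of the severity scale proves a prompted question was intended.* A followed-up event that has resolved can also be rated zero.

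None of these arguments supplies a scheduled question about other illness, a stated route for learning of a death, or an analysis of deaths and medical exits.

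**Conclusion.** The point holds in limited form. Spontaneous self-report is the only stated collection method, no adverse-event question is scheduled, no route to learn of a death is given, and contact after a missed monitoring visit is optional. A death, or a hospitalisation that leads to drop-out during abstinence, may therefore go unrecorded as an SAE and be counted as a relapse.

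The effect on the primary analysis is probably small: about one point of power for one or two cases. This rests on the assumed case counts, 157 events, a two-sided test and false events unrelated to the predictor. The documents give no rate of death or medical exit, so the number of false relapses cannot be estimated from them. The main issue is safety ascertainment, and the change is worth making because it is cheap. The results do not justify replacing the drop-out convention in the primary analysis.

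**What to change.** 1. **Collection and Recording of AEs and SAEs, and Table 2:** add one standard open question on new symptoms, illness or hospital care at each visit and at the 6- and 12-month calls.
2. **Monitoring Visits During 30-Day Abstinence Period:** make a contact attempt routine after every missed monitoring visit. Record timeline follow-back smoking and any medical event before drop-out status is assigned. Allowing use of the emergency contact when the participant cannot be reached would give a route for learning of a death.
3. **Primary Outcomes (Main Study) and the Aim 1 analysis:** keep drop-out as relapse in the primary analysis. Add a sensitivity analysis that censors documented deaths and medical exits at the last verified abstinent date, and state its non-informative censoring assumption.
4. **AE, SAE, and Unanticipated Problems Reporting:** start the 10-business-day clock when the team becomes aware of the event.

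The cost is protocol wording, one case report form item, one extra model run and some calls by existing staff. More minor events will be logged and some calls will go unanswered. Participants who cannot be reached stay under the current drop-out rule.
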